# 9.0 Study Withdrawal/Discontinuation

Participation in this study is voluntary. If at any time a study participant wishes to be withdrawn from the study, they may do so by contacting any of the key study personnel and letting them know they withdraw their consent. The date in which the participant withdraws their consent will be noted in their study file. Any information gathered up to the point of consent withdrawal may still be used for research and reporting.

Enrolled patients will be removed from the study if they are inconsistent with casting follow-up visits, noncompliant with treatment, or if the treating physician recommends TAL in the operating room due to specific patient factors, such as age or size.

# 10.0 Statistical Considerations

# **Power Analysis**

A power analysis was conducted to determine the sample size needed to find a clinically meaningful difference of 2.5 point in the FLACC score (SD=3) between the two methods. With alpha=0.05, power=0.8, and and effect size d=.83, at least 24 patients per group are required (N=48). Assuming a 20% participant lost to follow-up rate, we will need to enroll 29 patients per group (N=58).

An interim power analysis was conducted to determine the sample size to find a clinically meaningful difference of 2.0 points in the FLACC score between the two methods. This was performed using the maximum SD of the FLACC score observations of the first 39 patients (SD=4.13). With alpha=0.05 and power=0.8, at least 47 patients per group are required (N=94).

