#### **Electronic Consent Process:**

In the event a potential study candidate is missed during a clinic visit, or research personnel are unavailable to consent in-person, study personnel will contact the patient's parent(s)/legal guardian(s) by phone to notify them of their child's study eligibility and ask if they would be interested in their child taking part. If the parent(s)/legal guardian(s) are interested in their child taking part in the study, study personnel will send a link to the REDCap-based electronic consent form by e-mail. If the parent(s)/legal guardian(s) agree for their child to take part in the study after reading the informed consent document, there will be an option for one parent/legal guardian to electronically sign their name and date the informed consent document. Once they electronically sign the electronic informed consent document, they will be given an option to save or print the signed electronic informed consent documents for their files.

We will seek to enroll 47 patients per group, 94 patients total in this study at each site.

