# 6.0 Study Procedures

# Weekly Casting Visits

Once study consent is obtained, the subject will undergo serial casting weekly by one of two board-certified Pediatric Orthopaedic surgeons using the Ponseti method to address their congenital idiopathic clubfoot. CCLS will be present to provide coping support and standardize the environment. This is routine care at our institution. During these castings, patient will wear pulse ox on hand, with mitten covering tool if needed, in order to measure heart rate and oxygen saturation. The CCLS, with assistance from a trained research assistant, will assess the subject's pain and temperament utilizing observational data and data collected from FLACC Scale. Observational assessment is also routine care, but the FLACC data, pulse ox and temperament questionnaire are new, being collected strictly for the study. Primary data will be obtained during casting of first foot and, in the case of bilateral clubfoot patients, a subgroup will be created utilizing data collected during casting of both feet.

Data collection during weekly castings will be obtained by a trained research assistant and will be event based, utilizing pulse ox and FLACC scale. Time points are as follows:

- Baseline before cast placement (patient placed on treatment table)
- Start of casting, after cast padding placed (1st cast if bilateral)
- End of casting (2nd cast if bilateral)

If the subject does not require tenotomy after the weekly casting, they will be withdrawn from the study.

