# Data Analysis

FLACC, heart rate, and oxygen saturation will be measured at 10 distinct time points (Table 1) during serial casting and following in-office TAL. Changes in FLACC score, heart rate, and oxygen saturation will be compared between treatment and control cohorts utilizing a two-way ANOVA with a Geisser-Greenhouse correction for matched time measures. A Sidak's multiple comparisons test will be utilized to assess differences between cohorts at each of the 10 time points assessed. To compare number of

complications between cohorts, data will be collected at 3-weeks post TAL and analyzed using a non-parametric Mann-Whitney test, given the ordinal nature of the data. Similar non-parametric analysis with correction for multiple comparisons between cohorts will be utilized to assess changes in responses to REDCap surveys. Statistical analysis will be conducted utilizing GraphPad Prism 8.3.0. Statistical significance will be p<0.05.

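### The current target of 47 per group is both the number required and the number to enrol, with no loss allowance; the replaced allowance of 29 per group should have been 30

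*Combined protocol and SAP*

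**What the plan says.** The Power Analysis in Section 10.0 holds two calculations.

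- **Planning stage.** The target is a "clinically meaningful difference of 2.5 point in the FLACC score (SD=3) between the two methods". The result is given as "With alpha=0.05, power=0.8, and and effect size d=.83, at least 24 patients per group are required (N=48". The allowance follows: "Assuming a 20% participant lost to follow-up rate, we will need to enroll 29 patients per group (N=58".
- **Interim.** The difference becomes 2.0 points, and the SD becomes 4.13, the largest seen in the first 39 patients. The result is "With alpha=0.05 and power=0.8, at least 47 patients per group are required (N=94". No loss rate is given.

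The enrolment target closes the Electronic Consent Process text in Section 5.0: "We will seek to enroll 47 patients per group". The same sentence gives 94 in total and attaches that total to each site. The Enrollment text names two sites. Section 12.0 still ends the study once 24 per group (N=48) have completed follow-up.

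Consent comes before serial casting, and infants can leave after it. Section 6.0 says: "If the subject does not require tenotomy after the weekly casting, they will be withdrawn from the study". Section 9.0 also removes infants for inconsistent casting visits, for non-compliance, or when the physician recommends an operating-room procedure. Randomisation takes place on or after the final casting visit.

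**The concern.** A loss allowance should make the number left after loss equal the number the power calculation needs. The planning-stage allowance multiplies by 1.2, which falls slightly short of that.

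The interim calculation has no visible allowance. One paragraph earlier the plan separates the number required (24) from the number enrolled (29); for the current target the two are the same 47. Nothing says that the 20% assumption was withdrawn, and the plan itself provides for removing infants after consent. An infant removed before tenotomy has no tenotomy-day FLACC score. If 47 counts consented infants, the stated 80% power rests on more scores than the trial will have.

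**Working it through.** **Inputs.** From Section 10.0: alpha 0.05; power 0.80; 2.5 points with SD 3, then 2.0 points with SD 4.13; 20% loss, stated for the planning-stage calculation only. From Section 5.0: 1:1 allocation and 47 per group to enrol. The plan does not state sidedness. I assume a two-sided two-sample t-test, because 24 reproduces only that way (one-sided gives 19).

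**1. Reproducing 24 and 29.** d = 2.5/3 = 0.833 gives 23.6, so 24 per group. This agrees with the plan.
- 24 × 1.2 = 28.8, so 29; 48 × 1.2 = 57.6, so 58. These are the stated figures.
- Correct allowance: 24/(1 − 0.20) = 30 per group, N=60.
- 29 × 0.80 = 23.2 left, against 24 required. Power is 79.3% at 23.2 and 80.7% at 24, a cost of about 1.4 points.
- 29 is enough for losses up to 1 − 24/29 = 17.2%.

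**2. Allowance on the current target.** 47 enrolled − 47 required = 0.

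**3. Effect of loss if 94 is the study total and is counted from consent.** The column headed *47 taken as 80%* accepts the plan's claim and uses the effect size for which 47 per group gives 80% (d = 0.584). The last column uses the plan's own inputs, d = 2.0/4.13 = 0.484.

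| Loss | Left per group | Left in total | Power, 47 taken as 80% | Power at 2.0 points, SD 4.13 |
|---|---|---|---|---|
| 0% | 47 | 94 | 80% | 64% |
| 5% | 44.65 | 89.3 | 78% | 62% |
| 10% | 42.3 | 84.6 | 76% | 60% |
| 20% | 37.6 | 75.2 | 71% | 54% |

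**4. Why the last column starts at 64%.** Solving for n at d = 0.484, alpha 0.05 and power 0.80 gives 67.9, so 68 per group two-sided (54 one-sided). Neither is 47. For 47 to give 80% two-sided, the SD would have to be about 3.42 (2.0/0.584) or the difference about 2.41 (4.13 × 0.584). The gap from 80% to 64% therefore comes from the base number. Loss accounts only for the fall from 64% to 54%, at 20%.

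**5. If 94 are enrolled at each of two sites and pooled.** That is 94 per group. 94 × 0.80 = 75.2 remain, above both 47 and 68, and power at 2.0 points and SD 4.13 is about 84%.

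**The case against.** The 29-versus-30 difference is one infant per group in a calculation that no longer sets the target. Section 12.0 also defines the end of study by completers, so the 24 did not depend on enrolling 29. This stands; the figure is worth correcting only because it remains in the text and the method would understate any later target.

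Section 5.0, read literally, enrols 94 at each site. With two pooled sites there is no shortfall. This also stands as a possible reading. But Section 10.0 gives N=94 as the requirement and Section 12.0 gives N=48, so the documents do not settle it.

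The 20% was described as loss to follow-up. FLACC is recorded on the day of tenotomy, so an infant lost before day 21 can still contribute, and Section 9.0 allows data gathered before withdrawal of consent to be used. Infants who turn out not to need a tenotomy should leave before randomisation, so if 47 counts randomised infants, those withdrawals do not reduce it. All of this is fair. It makes 20% an assumption for the current target, which is why a range is shown. It does not remove the point, because Section 5.0 speaks of enrolment, and removals before tenotomy do cost FLACC scores if counting starts at consent.

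**Conclusion.** The point holds in two parts of unequal weight. The allowance of 29 (N=58) should be 30 (N=60), a minor error in a replaced calculation. The current target carries no loss allowance, because 47 is both required and enrolled while the plan allows removals after consent. If 94 is the study total and enrolment is counted from consent, any loss before tenotomy leaves fewer than 47 per group. Taking the plan's 80% at face value, 5% to 20% loss costs roughly 2 to 9 points of power.

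Three stronger readings are tempting and are not supported:

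- A reader might infer that the missing allowance brings power down from 80% to 54%. It does not: power is already 64% with nobody lost, because 47 does not follow from 2.0 points and SD 4.13.
- A reader might infer that neither stated size can deliver its evaluable number. For the current target that depends on 94 being the study total; under the per-site reading it is not so.
- A reader might infer that dividing 47 by 0.8 repairs the plan. That would put an allowance on a base that does not give 80% power at the stated inputs.

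The figures assume a two-sided two-sample t-test. The loss rates for the current target are illustrative, since the interim paragraph gives none.

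**What to change.** 1. In Section 10.0, correct 29 (N=58) to 30 (N=60).
2. Reconcile Section 5.0 (94 at each site), Section 10.0 (N=94) and Section 12.0 (N=48): state whether 94 is the study total or per site.
3. State whether 47 per group counts consented infants, randomised infants, or infants with a tenotomy-day FLACC score.
4. If 94 in total is kept, give the expected number with a tenotomy-day FLACC score as enrolment × (1 − loss) over a stated range (about 75 at 20%), and the power at that number from 2.0 points and SD 4.13, in place of 80%.

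If the sponsor prefers to enlarge the trial to keep 80% at those inputs, the calculation should start from 68 per group with scores, not 47, and divide by one minus the assumed loss.

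Items 1 to 4 cost restated text in Sections 5.0, 10.0 and 12.0, with no change to procedures. If 94 is the total, the stated power becomes less favourable.

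### Section 10.0 calls both 2.5 and 2.0 points the clinically meaningful FLACC difference without saying which governs or why, and at the interim SD 47 per group gives 64% power for 2.0, not the stated 80%

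*Combined protocol and SAP*

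**What the plan says.** The Power Analysis in Section 10.0 has two paragraphs, both in the current text.

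- The original calculation aims to "find a clinically meaningful difference of 2.5 point in the FLACC score (SD=3) between the two methods". With alpha 0.05 and 80% power it arrives at 24 per group, raised to 29 for a 20% loss to follow-up.
- The interim calculation aims to "find a clinically meaningful difference of 2.0 points in the FLACC score between the two methods". It was done "using the maximum SD of the FLACC score observations of the first 39 patients (SD=4.13"). Its result is: "With alpha=0.05 and power=0.8, at least 47 patients per group are required (N=94"). No allowance for loss is mentioned.

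The interim paragraph does not refer back to 2.5, does not withdraw it, and gives no clinical argument for 2.0.

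Elsewhere, Section 5.0 (end of the Electronic Consent Process) takes up the interim number: "We will seek to enroll 47 patients per group, 94 patients total in this study at each site". Section 12.0 still ends the study at 24 per group, the number from the 2.5-point calculation. The Data Analysis part of Section 10.0 judges results at p<0.05 and names no FLACC difference.

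**The concern.** The outcome, the comparison and the label are the same in both paragraphs, but the value differs. The only new information reported at the interim is a standard deviation. That is a sound reason to recalculate the sample size, but it says nothing about how large a difference matters for an infant. A reader cannot tell whether 2.0 replaced 2.5 on clinical grounds, or whether 2.5 still stands.

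The choice affects what the trial can claim. At the interim SD the two values fall on opposite sides of what 47 per group can detect with 80% power. If 2.0 is the design difference, as the order of the text suggests, the stated power is too high. Aim 1 in Section 2.0 expects the J-Tip to be at least as good as the cream, so a small or null difference is a plausible result, and the stated power will be used to judge how informative it is.

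**Working it through.** **Inputs** (Section 10.0, Power Analysis): differences 2.5 and 2.0 points; SD 3 (original) and 4.13 (interim); alpha 0.05; power 0.80; loss 20% (original paragraph only). Allocation is 1:1 (Section 5.0). Sidedness is not stated; two-sided is assumed.

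**Formulas** for a two-sample comparison of means:

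- n per group = 2 × (1.960 + 0.842)² × SD² / Δ² = 2 × 7.85 × SD² / Δ²
- SE = SD × √(2/n)
- power ≈ Φ(Δ/SE − 1.960)

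These are normal approximations. The exact two-sample t-test adds about one patient per group and is the result used below.

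**Step 1: reproduce the original 24.** Δ = 2.5, SD = 3: 2 × 7.85 × 9 / 6.25 = 22.6, so 23; the t-test gives 23.6, so 24. The stated figure is reproduced, which supports the two-sided t-test as the method.

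**Step 2: try to reproduce the interim 47.** Δ = 2.0, SD = 4.13 (SD² = 17.06): 2 × 7.85 × 17.06 / 4 = 67 (t-test 67.9, so 68). A one-sided test gives 54. A Mann-Whitney efficiency adjustment raises the two-sided figure to about 71, and a paired test gives 36. None gives 47. For 2.0 points, 47 per group fits an SD of about 3.42, or power of about 65%.

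**Step 3: the same SD with 2.5 points.** 2 × 7.85 × 17.06 / 6.25 = 42.8, so 43; the t-test gives 43.8, so 44.

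**Step 4: power at 47 per group.** SE = 4.13 × √(2/47) = 0.852.

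- Δ = 2.0: 2.0/0.852 − 1.960 = 0.39, power 65% (t-test 64%).
- Δ = 2.5: 2.5/0.852 − 1.960 = 0.97, power 84% (t-test 83%).
- Difference with 80% power (t-test): 2.41 points.

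**Step 5: sensitivity** (two-sided t-test):

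| Situation | Power for 2.0 | Power for 2.5 |
|---|---|---|
| 47 evaluable per group, SD 4.13 | 64% | 83% |
| 20% loss: 47 × 0.8 = 37.6, so 37 evaluable | 54% | 73% |
| Target applies to each of two sites: 2 × 47 = 94 per group | 91% | 98% |
| 47 per group, SD 3 | 89% | 98% |
| 47 per group, SD 4.13, Sidak over 10 time points: alpha = 1 − 0.95^(1/10) = 0.0051 | 31% | 53% |

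A one-sided test at 47 per group and SD 4.13 gives 75% for 2.0 and 90% for 2.5, so even then 2.0 does not reach 80%.

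**The case against.** The best defence is that Section 10.0 reads in sequence: an original calculation, then an interim one that updates it. Section 5.0 adopts the interim number. On this reading 2.0 is simply the current value and 2.5 is history. That is the natural reading, and it stands. It would be too strong to infer that the design difference is undefined; what is missing is a sentence saying that 2.0 supersedes 2.5, and a reason. This reading also makes the power statement worse, because 2.0 is the value for which 47 falls short.

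A reader might also infer that an observed difference between 2.0 and 2.5 points would be meaningful under one paragraph and not under the other. The plan contains no such rule. The Data Analysis text uses p<0.05 only, and nothing compares an estimate or interval with either value.

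A third tempting inference is that the difference was lowered in response to the results. The documents report only an SD from the 39 patients; nothing indicates that group differences were examined. A smaller target difference is, if anything, the more demanding choice.

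Finally, the interim used the maximum SD, so power is higher wherever the SD is smaller, and the wording in Section 5.0 may mean 47 per group at each site. Both points are fair. They limit the shortfall to stated conditions but do not rescue the stated calculation, which claims 80% at SD 4.13 with 47 per group.

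**Conclusion.** The point holds in a limited form. Section 10.0 gives two clinically meaningful differences for one comparison and does not connect them. The interim SD supports a new sample size but not a new difference. If 2.0 is current, as the later paragraph and Section 5.0 suggest, 47 per group gives 64% power rather than 80%, and 68 per group would be needed. With 47 per group, power reaches 80% only for differences of about 2.4 points or more.

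This rests on SD 4.13, a two-sided alpha of 0.05, 47 evaluable per group in the whole trial, and a single unadjusted comparison. With the protocol's own 20% loss, neither difference reaches 80% (54% and 73%). With 94 per group over two sites and no loss, both do.

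The documents do not support going back to 2.5 merely because 47 suffices for it. They give no clinical source for either value, and choosing the one that fits the existing sample size would also be a choice made after the interim SD was known.

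**What to change.** In Section 10.0, Power Analysis:

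1. Name one clinically meaningful FLACC difference, say that it supersedes the other, and give the clinical reason.
2. Restate the power at 47 evaluable per group and SD 4.13 for that value: 64% for 2.0 points or 83% for 2.5 points, described as applying to a single unadjusted two-sided comparison.
3. Put the power after the expected loss beside it. At 20% loss (about 37 evaluable) this is about 54% for 2.0 or 73% for 2.5.

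In Section 5.0, state whether 47 per group is the trial total or the target at each site; if it is per site, recompute the power figures for the trial total. Section 12.0 should then carry the same target in place of 24 per group.

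The cost is a few sentences and no extra patients. The downside is a less favourable stated power if 2.0 is kept, or a larger stated detectable difference if 2.5 is chosen.

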# 5.0 Enrollment/Randomization

#### **Enrollment**

General inclusion/exclusion criteria will be used to determine patient eligibility for this study. Potential study participants will be identified when they present to the Vanderbilt Children's Orthopaedic or Texas Scottish Rite Hospital for Children clinics for treatment of presumed congenital idiopathic clubfoot.

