# 12.0 Follow-up and Record Retention

The duration of this study will last until we have enrolled and completed follow-up on 24 patients per group (N=48). All study data will be maintained for 6 years following study completion. Following this 6 year period, the Redcap database will be archived and all physical study forms will be disposed of in shred-it confidentiality bins provided by VUMC.

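### The revised sample size of 47 per group does not follow from its printed inputs, which need 68 per group (54 one-sided), and the trial total is stated in three incompatible ways

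*Combined protocol and SAP*

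**What the plan says.** Section 10.0 (Power Analysis) contains two calculations.

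- The first uses 2.5 FLACC points, SD 3 (d = 0.83), alpha 0.05 and power 0.8, and arrives at 24 per group. It then allows for loss: "Assuming a 20% participant lost to follow-up rate, we will need to enroll 29 patients per group (N=58").
- The second, called an interim power analysis, targets a "clinically meaningful difference of 2.0 points in the FLACC score between the two methods". On the SD it says: "This was performed using the maximum SD of the FLACC score observations of the first 39 patients (SD=4.13"). It concludes: "With alpha=0.05 and power=0.8, at least 47 patients per group are required (N=94"). It names no test, sidedness, correlation or loss allowance.

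The size of the trial appears in two other places.

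- Section 5.0, at the end of the Electronic Consent Process text: "We will seek to enroll 47 patients per group, 94 patients total in this study at each site". The Enrollment text of the same section recruits from the Vanderbilt clinics and from "Texas Scottish Rite Hospital for Children clinics for treatment of presumed congenital idiopathic clubfoot".
- Section 12.0: "The duration of this study will last until we have enrolled and completed follow-up on 24 patients per group (N=48").

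Section 10.0 (Data Analysis) plans a repeated-measures two-way ANOVA: "Changes in FLACC score, heart rate, and oxygen saturation will be compared between treatment and control cohorts". It gives no within-infant correlation.

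**The concern.** The target difference fell from 2.5 to 2.0 points and the SD rose from 3 to 4.13, so the standardised effect fell from 0.83 to 0.48. Sample size varies with the inverse square of that effect, so it should rise by a factor of nearly three. The plan's figure only about doubles, from 24 to 47.

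The plan claims 80% power for a difference it calls clinically meaningful. If the true power is lower, a null result is more likely to be a miss than the reader is told. This matters for Aim 1, whose hypothesis is that J-Tip is equal to or better than the cream: a non-significant result could easily be read as equality.

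The three totals make it worse. Until it is clear which one governs, nobody can say what power the trial has, and section 12.0 read literally ends the trial at about half of the revised number.

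**Working it through.** **Inputs.** From section 10.0: difference 2.0, SD 4.13, alpha 0.05, power 0.80. From section 5.0: 1:1 allocation. The standardised effect is d = 2.0 / 4.13 = 0.484.

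**Step 1: reproduce the first calculation.** A two-sided two-sample t-test (noncentral t) with d = 0.83 needs 23.8, so 24 per group, as printed; power at 24 is 0.804. A one-sided test would need 18.7, so 19. The plan's own benchmark is therefore the two-sided t-test.

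**Step 2: apply the same method to the revised inputs.**

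- Normal approximation: n = 2 (1.960 + 0.842)² × 4.13² / 2.0² = 66.9, so 67 per group.
- Noncentral t, two-sided: 67.9, so **68 per group (N = 136)**.
- Noncentral t, one-sided 0.05: 53.4, so **54 per group (N = 108)**.

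**Step 3: look for a reading that gives 47.**

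- Paired or one-sample t-test: 36.
- Old difference of 2.5 with SD 4.13: 44.
- Sidak-adjusted alpha for 10 comparisons: 116.
- Two-sided, 47 per group has 80% power for a difference of 2.41 at SD 4.13, or for 2.0 points at SD 3.42.
- A baseline correlation could also give 47. The required variance ratio is (3.424 / 4.13)² = 0.687. For ANCOVA, 1 − ρ² = 0.687 gives ρ = 0.56. For change scores with equal SDs, 2(1 − ρ) = 0.687 gives ρ = 0.66. For a mean over ten equally correlated time points, (1 + 9ρ)/10 = 0.687 gives ρ = 0.65.

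The documents state none of these inputs for the revised calculation.

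**Step 4: power for 2.0 points at SD 4.13, by stated total.**

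| Source | Per group | Power, two-sided | Power, one-sided | Difference detectable with 80% power, two-sided |
|---|---|---|---|---|
| Section 12.0 (N = 48) | 24 | 0.38 | 0.50 | 3.41 |
| Section 10.0 (N = 94) | 47 | 0.64 | 0.75 | 2.41 |
| Section 5.0, two sites pooled (2 × 94 = 188) | 94 | 0.91 | 0.95 | 1.70 |

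**Step 5: sensitivity to the SD.** The plan describes 4.13 as a maximum. At 47 per group, two-sided power is 0.89 with SD 3, 0.80 with SD 3.42, 0.71 with SD 3.8 and 0.64 with SD 4.13.

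**Step 6: losses.** The first calculation raised 24 to 29. The revised one states no allowance, and the same 47 is the number required in section 10.0 and the number to enrol in section 5.0. For illustration only: if 20% of 47 were not evaluable (37 or 38 left), two-sided power at SD 4.13 would be 0.54 to 0.55.

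**The case against.** The arithmetic is hard to dispute, but several points limit what follows from it.

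- **Underpowering is conditional.** Power of 0.64 requires that 94 is the whole trial, that SD 4.13 applies and that the test is two-sided. Section 5.0 read literally gives 94 per group over two sites and power of 0.91. An SD chosen as the maximum observed is cautious. This stands, and the conclusion is worded to respect it.
- **The hypothesis is directional.** A one-sided test would have power 0.75 at 47 per group. That is still below 0.80, and the required number would be 54. Two-sided remains the natural reading because only it reproduces the first calculation.
- **The planned analysis uses changes and repeated measures**, so a correlation may have entered the calculation. That is possible, but none is printed, so 47 cannot be checked.
- **The 48 in section 12.0 looks like a leftover** from the first calculation. Probably so, but it is current text and states when the study ends.
- **Infants who turn out not to need a tenotomy** (section 6.0, Weekly Casting Visits) should normally leave before randomisation, which section 5.0 places on or after the final casting visit. They would not then reduce the randomised groups. This is fair as far as it goes. However, the schedule puts consent at the enrolment visit, and section 9.0 speaks of enrolled patients being removed for missed casting visits or because the tenotomy is moved to the operating room. What the 47 counts is therefore still undefined.
- **The 20% loss figure has no support in the revised calculation**, and procedural FLACC scores are taken on the day of tenotomy, so loss during the later surveys does not remove them. Agreed: it carries no weight in the conclusion.

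**Conclusion.** The concern holds. With the inputs printed in section 10.0, 80% power requires 68 evaluable infants per group (two-sided) or 54 (one-sided), not 47. Neither rounding nor sidedness closes the gap, and no stated correlation or adjusted SD does so.

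If 47 per group is the whole trial and SD 4.13 applies, the chance of missing a true 2.0-point difference is about 36% (1 − 0.64) rather than 20%. If 94 per group are recruited over two sites, the trial exceeds its target. What is established is that the stated power cannot be derived from the stated inputs, and that current text supports three totals whose two-sided power runs from 0.38 to 0.91. The figures assume two independent groups, 1:1 allocation, a t-test and no gain from baseline or repeated measurements. This must be corrected.

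**What to change.** Correct the second paragraph of the Power Analysis in one of three ways:

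1. Keep 47 evaluable infants per group and state that this gives about 64% power for 2.0 points at SD 4.13, or 80% power for about 2.4 points.
2. State that the listed inputs require 68 evaluable infants per group.
3. State the test, the sidedness and the further input (for example a baseline correlation, with its source) that produced 47.

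Then reconcile the total:

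- Say in sections 5.0 and 10.0 whether 94 is the whole trial or the number per site.
- Replace the 24 per group (N = 48) in section 12.0.
- Give the power for the total that applies.
- Say whether the number counts consented, randomised or evaluable infants, and state the loss allowance, including if it is none.

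The cost is wording in three sections. No extra infants are needed if the existing total is kept, though the stated power becomes less favourable if 94 is the whole trial. Choosing 68 per group would add 136 − 94 = 42 evaluable infants to a total of 94.
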